**Teaching Academic Success Skills to Students with Autism Spectrum Disorders in the
Clinical Setting**

Study Protocol and Statistical Analysis Plan

Clinical Trials.gov Identifier: NCT03606343

September 22, 2020

STUDY PROTOCOL

PURPOSE OF STUDY:

The goal of the study is to develop an academic EF intervention, *Achieving/Academic Independence in Middle School (AIMS)*, for high functioning (i.e., IQ score ≥ 80) middle-school youth with ASD and EF deficits. The primary aim is to: Examine the feasibility and acceptability of AIMS in a series of open trials (n=21) including the feasibility of: 1) implementing the measurement protocol, 2) operationalizing intervention delivery, 3) assessing both trained and untrained areas of functioning, 4) assessing whether improvements in academic EF skills (*proposed mechanism of treatment*) are related to functional educational outcomes (e.g., homework behaviors, grades), and 5) exploring the data for potential treatment moderators (e.g., gender, severity). It is hypothesized that AIMS will be feasible, acceptable (attendance, satisfaction), and will result in improved academic EF skills associated with reduced academic impairment and homework problems.

STUDY DESIGN:

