Open Trial: To document proof of concept and gather sufficient preliminary data for a future RCT, 3 cohorts of youth with ASD (n=21) will be recruited (three groups will be recruited to participate in the group intervention; the maximum group size for this intervention is 7 based on the level of individualized attention needed during the intervention). A research assistant will observe all sessions and complete treatment fidelity checklists to monitor adherence. Sessions will also be videotaped for later use (e.g., training, fidelity coding). The primary teacher will complete organization and time management checklists weekly. We do not anticipate making major changes to the intervention during the open trials; however, as needed the intervention manual may be refined to be clearer. Parent(s) and their teen will attend 7 intervention sessions offered 1 week apart at CCHMC. Session content will include psychoeducation about the academic EFs in ASD and will be taught strategies and skills targeting these deficits, including using a behavioral contract (i.e., Agreement), organization skills (e.g., homework system, binder organization, etc.), time management skills (e.g., planner), problem solving skills, and study skills (e.g., flash cards). We will also be doing midweek check-ins with parents during the intervention to increase accountability and coach parents as needed.

Post Assessment and Exit Interviews: The primary measures collected will be treatment fidelity and academic EF skills acquisition, although other measures will be collected to pilot these measures and methods for collection and to gather information about whether they capture gains made by families. Parents and youth with ASD will also be surveyed regarding their experience of the intervention and whether they understood intervention materials in exit interviews.

Consultation with Experts: A webinar will be scheduled to process the information obtained during the open trial, including the feedback from the parents, and youth obtained in the exit interviews, the fidelity ratings, the utility and feasibility of the proposed measures.

Finalize Intervention Manual: A finalized draft of the manual will be developed including sections on troubleshooting, treatment rationale, strategies for specific skills, case examples, and

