Descriptive statistics will summarize attendance, satisfaction (AIQ), fidelity, drop-out rates, exit interview data to assess feasibility and acceptability. Within group (pre-test, post-test) mixed factorial ANCOVAs controlling for pre-test scores will test for the presence of improvements. It is hypothesized that youth with ASD will demonstrate improved academic EF skills (BRIEF-2, COSS, HPC). The primary analytic focus will be on evaluating whether the observed effect sizes across outcomes warrant continued study of AIMS as a treatment strategy. A moderate (i.e., Cohen's $d = .5$ ⁸¹) effect size for academic EF measures will be evidence of significant improvement. We will explore whether AIMS improves academic (WJ, CPS, APRS), and parent-child relationship (PRQ) outcomes between pre- and post- assessments. Correlations between changes in academic EF skills and changes in the other outcomes measures will also be computed to explore whether changes in academic EF skills are related to functional academic outcomes, as these are the primary target and proposed mechanism of treatment.

Exploratory Analyses: We will also explore potential moderators such as sex, IQ, ASD and EF severity, and socioeconomic status qualitatively and with non-parametric statistics given the lack of power.

References

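### The SAP calls an observed d of .5 evidence of significant improvement, which a point value cannot show, and it places the Homework Problems Checklist in a different domain from the rest of the protocol

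*Combined protocol and SAP*

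**What the plan says.** The Statistical Analysis Plan section makes two separate statements about improvement. First, pre-post "mixed factorial ANCOVAs controlling for pre-test scores will test for the presence of improvements". Second, the main analytic focus is on "evaluating whether the observed effect sizes across outcomes warrant continued study of AIMS as a treatment strategy", and a moderate (d = .5) "effect size for academic EF measures will be evidence of significant improvement". The section gives no alpha, sidedness, confidence interval, divisor for d, or rule connecting d to the ANCOVA result. It does not say which scores or raters the benchmark covers, or how several scores combine.

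The same section lists the academic EF measures as "improved academic EF skills (BRIEF-2, COSS, HPC". The academic outcomes come separately: "We will explore whether AIMS improves academic (WJ, CPS, APRS), and parent-child relationship (PRQ) outcomes". HPC is therefore on the EF list and absent from the academic list.

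The rest of the protocol treats homework differently. The Purpose of Study asks whether gains in academic EF skills "are related to functional educational outcomes (e.g., homework behaviors, grades", and hypothesises that AIMS "will result in improved academic EF skills associated with reduced academic impairment and homework problems". The Measures section places HPC under Academic Functioning. Table 1 gives HPC domain code A (academic outcome), while BRIEF-2 and COSS carry code EF. Under Post Assessment and Exit Interviews: "The primary measures collected will be treatment fidelity and academic EF skills acquisition".

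**The concern.** Academic EF is a named primary measure, effect sizes are the basis for deciding on further study, and .5 is the only numerical benchmark in the SAP. If .5 is meant as a magnitude benchmark, *significant* is the wrong word. If statistical significance is meant, a point value cannot deliver it. As written, a mean change whose 95% CI includes zero could be reported as significant.

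The set of scores behind the benchmark is also open. BRIEF-2 has two raters and COSS has three, and HPC adds a sixth score if it counts as EF. A way of combining them chosen after the data are seen could decide the conclusion.

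HPC's domain also affects the correlations between EF change and change in other outcomes. HPC is the only instrument the documents describe as measuring homework problems. If it sits on the EF side, the outcomes left to correlate with EF change are WJ, CPS, APRS and PRQ, and none of these is described as a homework measure.

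**Working it through.** The plan gives no sample-size, power or alpha calculation, so there is no figure to reproduce.

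**Inputs from the documents.** Planned n = 21, single arm (Open Trial). Benchmark d = .5 (SAP). Raters: BRIEF-2 two, COSS three, HPC one (Measures, Table 1).

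**Assumptions, not in the documents.** Two-sided .05; a paired t-test standing in for the ANCOVA, whose model is not written out; equal pre and post SDs; 17 to 21 completers; pre-post correlation r of .3 to .7.

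**Step 1: d divided by the SD of change.** t = d × √n on n − 1 df, with a noncentral-t interval for d.

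| Completers | t | two-sided p | 95% CI for d | smallest d with p < .05 |
|---|---|---|---|---|
| 21 | .5 × √21 = 2.29 | .033 | 0.04 to 0.95 | .455 |
| 18 | .5 × √18 = 2.12 | .049 | 0.00 to 0.99 | .497 |
| 17 | .5 × √17 = 2.06 | .056 | −0.01 to 1.00 | .514 |

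**Step 2: d divided by the baseline SD, 21 completers.** The SD of change is √(2(1 − r)) baseline SDs, so d on the SD of change is .5/√(2(1 − r)).

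| r | d on SD of change | t | two-sided p |
|---|---|---|---|
| .3 | .5/1.183 = .423 | 1.94 | .067 |
| .4 | .5/1.095 = .456 | 2.09 | .049 |
| .7 | .5/0.775 = .645 | 2.96 | .008 |

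At r = .3 the 95% CI for mean change is .5 ± 2.086 × 1.183/√21 = −0.04 to 1.04 baseline SDs. The break-even r is about .40.

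**Step 3: sensitivity to the test.** One-sided, the two failing cases pass (.028 at n = 17 on the SD of change; .034 at n = 21, r = .3 on the baseline SD). If the ANCOVA regresses change on the sample-centred pre-test, the residual SD is SD × √(1 − r²) × √((n − 1)/(n − 2)) with n − 2 df. Then n = 17 with r = .5 gives .5/(.894/√17) = 2.31, p = .036. The case n = 21 with r = .3 gives .5/(.979/√21) = 2.34, p = .030. By simulation (n = 21), that version rejects in 7% (r = .7) to 11% (r = .3) of trials with no true change, because it ignores sampling error in the baseline mean.

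**Step 4: how scores combine (illustration).** Six rater-level scores, n = 21, SD of change, assumed inter-correlation ρ of .2 to .5, true d = .2 on each. By simulation, the mean of the six d values reaches .5 in 2–5% of trials and the d of a composite in 16–26%; at least one score reaches it in 33–42%. The composite differs from the mean because averaging removes noise: its true d is .2 × √(6/(1 + 5ρ)), which is .35 at ρ = .2 and .26 at ρ = .5. With no true change, at least one of six separate 95% CIs lies wholly on the side of improvement in 11–13% of trials, against 2.5% for a single score.

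**Step 5: HPC's place.**

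| Location | Placement |
|---|---|
| SAP, hypothesis on EF | academic EF |
| SAP, list of academic outcomes | absent |
| Measures | under Academic Functioning |
| Table 1 | code A |
| Purpose of Study | homework is an outcome related to EF gains |

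**The case against.** The SAP gives testing to the ANCOVAs, then turns to observed effect sizes and cites a standard reference for *moderate*. Read in that order, .5 is naturally a magnitude benchmark and *significant* is loose wording. Both results would be reported, so a reader could see any gap. This is also a feasibility trial. These points stand and limit the seriousness, but the text does not say that it means magnitude, and the correction is small.

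A reader might infer that d = .5 generally fails to be significant here. The documents do not support that. With all 21 completers and d on the SD of change it is significant, and slightly stricter than the test, which needs only .455. The failing cases require dropout, or a baseline-SD divisor with r below about .40, and both pass one-sided or under the ANCOVA form in Step 3.

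A reader might also infer that the plan would claim success if any one score reached .5. No such rule is stated. Step 4 shows only that an unstated choice matters.

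Finally, a reader might infer that homework drops out of the study if HPC counts as EF. It does not: HPC is still collected and tested pre and post, and CPS still covers academic impairment. What is affected is the set of scores behind the .5 benchmark and the exploratory correlation with homework.

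**Conclusion.** The point holds in a conditional form. The same observed d of .5 falls on either side of two-sided .05 depending on matters the SAP leaves open: p = .033 with 21 completers and .056 with 17 on the SD of change, and .067 (r = .3) to .008 (r = .7) with 21 completers on the baseline SD. These figures rest on the assumed alpha, sidedness, paired test, equal SDs, completer numbers and correlations. The sentence is therefore wrong as a statement about significance, although its conclusion will often coincide with a test.

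The HPC mismatch needs no assumptions, because the sections disagree on the page. Its effect is confined to the benchmark set and the exploratory EF-homework correlation. Both matters are worth correcting; neither invalidates the study.

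**What to change.** 1. Describe d of .5 or more as a promising magnitude. Use *significant* only for the result of one named pre-post analysis of mean change, with the 95% CI taken from that same analysis so that test and interval cannot disagree. If an ANCOVA is kept for this, write out the model and allow for sampling error in the baseline mean.
2. Report each d with its CI, the number of completers and one stated divisor.
3. Put HPC in one domain throughout. Classing it as an academic outcome, in line with the Purpose of Study, the Measures section and Table 1, keeps a homework outcome for the correlations.
4. Before the data are seen, name the scores and raters that enter the benchmark and one combined summary, for example a composite. Apply both the .5 benchmark and the word *significant* to that summary, and show individual scores as supportive. The sponsor should choose the summary knowing that .5 on a composite is an easier target than a mean d of .5 (Step 4).

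Possible wording, once the sponsor has filled in the named items: *A pre-post d of at least .5 on [named summary of named academic EF scores], divided by [named SD], will be regarded as a promising magnitude. Improvement on that summary will be called significant only if [named analysis] gives a 95% CI for mean change that excludes zero in the direction of improvement. Individual scores will be shown with d, 95% CI and number of completers as supportive results.*

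The cost is a few SAP sentences and less freedom to choose among scores afterwards. Using one summary avoids the 11–13% chance of at least one favourable interval among six when nothing has changed. The change does not cure the low precision at n = 21, where the interval around d = .5 still runs from 0.04 to 0.95.

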guidance for establishing and maintaining effective relationships with participants⁶⁸ will be incorporated. Finalized graphics and storyboards will be selected and scripts revised for the animated clips depicting important content.

Participants

Youth with ASD: The target population is high functioning middle school youth (6, 7, and 8th graders ages 10 to 14) who have an educational label of Autism (e.g., school referred) and/or meet diagnostic criteria for ASD (e.g., clinic referred). In cases where it may need to be clarified (e.g., youth attends a specialized school for ASD, or the child is in an intermediate school), we will confirm that youth transition between teachers for core academic subjects. For research purposes, the diagnosis of all youth will be confirmed using the ADOS-2. All participants with ASD will present with EF problems based on the parent or teacher rated BRIEF-2 T-Score >60 on the Planning, Organization, or Monitor subscales.

An IQ score ≥ 80 will be required in order to select a high functioning population that will be most likely to profit from the intervention and are more likely to be in the mainstreamed educational environment or be eligible for mainstreaming.

Youth in middle school (typical age range 10 to 14) attending public or private middle/junior high schools will be recruited. Youth receiving pullout special education services for the majority of the day will be excluded because services required for those individuals would exceed that which AIMS could address. Additionally, those who receive significant support in the classroom (e.g., one-on-one aide for the whole school day) may not benefit from the intervention given its focus on promoting independence and initiative; this will be verified by reviewing the IEP.

Both sexes will be represented although more males than females (4:1 ratio) are anticipated given prevalence data for ASD⁶⁹.

Parents/Caregivers of Youth with ASD: Since parents/caregivers will be critically involved in implementing and reinforcing the intervention components, their input will be invaluable. Parents will be the primary caregiver of a child with high functioning ASD, English-speaking, and be willing and able to attend the intervention sessions.

Expert Consultants: An expert panel of consultants with expertise in academic issues facing youth with ASD and with developing and implementing school-based interventions will provide feedback on the final manual.

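### A single-arm pre-post study of 21 can describe predictors of change but cannot identify treatment moderators, and lack of power is not a reason for non-parametric statistics

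*Combined protocol and SAP*

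**What the plan says.** The Purpose of Study states the primary aim as "Examine the feasibility and acceptability of AIMS in a series of open trials (n=21"), and its fifth component is "exploring the data for potential treatment moderators (e.g., gender, severity"). Under Study Design (Open Trial), "3 cohorts of youth with ASD (n=21) will be recruited", and "the maximum group size for this intervention is 7". No control or comparison group is described in any section. The same paragraph says that the study is meant to supply preliminary data for a later RCT.

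The Statistical Analysis Plan compares pre-test with post-test within the one group. Its Exploratory Analyses paragraph then covers "potential moderators such as sex, IQ, ASD and EF severity, and socioeconomic status qualitatively and with non-parametric statistics given the lack of power". It names no particular test, significance level, multiplicity rule or rule for keeping or discarding a factor. Under Participants, "more males than females (4:1 ratio) are anticipated", and entry requires a parent- or teacher-rated BRIEF-2 T-score above 60 on one of three subscales. Table 1 shows the BRIEF-2 at eligibility and at post only, so the score used for selection is also the baseline.

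**The concern.** A treatment moderator is a factor across which the effect of treatment, compared with no treatment, differs. One treated arm yields only the change seen under AIMS. If girls change more than boys, AIMS may work better in girls, or girls may have changed more over those weeks anyway. Nothing collected in this study tells the two apart.

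The plan discloses one limitation, low power, and this points the reader the wrong way: it suggests that a larger sample would answer the question, when only a comparator would. The wording also makes non-parametric statistics look like a response to low power. At stake is what the report may say about component 5 of the aim, and how far a later trial team may lean on it.

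**Working it through.** **Inputs.** From the documents: n = 21, three cohorts, maximum group size 7, 4:1 male to female, one arm, pre-post analysis. Assumed, because the documents give no value: two-sided 5% level, all 21 analysed, equal SD of change in the groups compared. The d = 0.5 benchmark ("effect size for academic EF measures will be evidence of significant improvement") concerns mean pre-post change in academic EF and is not a target for any moderator.

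**The plan's own figure.** 3 × 7 = 21. The sample size is reproduced as group capacity; no power calculation is stated.

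**Identification.** Write the expected pre-post change in group g as Δg = τg + υg, where τg is the effect of AIMS and υg is the change without it. Then

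Δgirls − Δboys = (τgirls − τboys) + (υgirls − υboys).

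Moderation is the first bracket. One arm estimates only the sum. The second bracket does not shrink as n grows, and perfect measurement does not remove it. The same holds for slopes on IQ, ASD severity or SES. A control arm would estimate the υ terms, and the treatment-by-factor interaction would then isolate the first bracket.

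**EF severity.** Here a further artefact arises. Suppose there is no treatment effect, test-retest reliability is ρ, and pre and post variances are equal. The correlation of baseline with change is −√((1−ρ)/2): −0.22 at ρ = 0.9, −0.32 at 0.8, −0.39 at 0.7 and −0.45 at 0.6. In 20,000 simulated samples of 21, a Spearman test was significant in 15%, 26%, 37% and 48% of them. The reliabilities are assumed and the entry cut-off was not applied. Truncating the baseline range would weaken this correlation without abolishing it, while selection on a high score adds regression of the group mean.

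**Precision, sex.** Expected girls: 21 × 1/5 = 4.2. With Binomial(21, 0.2), P(2 or fewer) = .009 + .048 + .121 = .18. The 95% CI half-width, in SDs of change, is t(.975, 19) × √(1/n₁ + 1/n₂):

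- 4 v 17: 2.093 × √(1/4 + 1/17) = 2.093 × 0.556 = 1.16
- 2 v 19: 2.093 × √(1/2 + 1/19) = 2.093 × 0.743 = 1.56
- 6 v 15: 2.093 × √(1/6 + 1/15) = 2.093 × 0.483 = 1.01

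**Precision, correlation.** By Fisher's z, the half-width at r = 0 is tanh(1.96/√18) = tanh(0.462) = .43. An observed r of 0.30 has a 95% CI of about −0.15 to 0.65.

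**Do non-parametric statistics help power?** The plan names no test, so the exact Mann-Whitney test serves as an illustration. The table gives power for a 1.0 SD difference in 20,000 simulations:

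| Distribution of change | 17 v 4: t-test | 17 v 4: rank | 11 v 10: t-test | 11 v 10: rank |
|---|---|---|---|---|
| Normal | 40.6% | 34.5% | 58.2% | 53.1% |
| Laplace | 43.4% | 44.0% | 61.1% | 64.5% |
| t(3) | 51.6% | 54.8% | 69.5% | 76.5% |
| Lognormal | 58.8% | 76.7% | 74.4% | 90.9% |

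The rank test loses somewhat under normality, about equals or modestly beats the t-test under Laplace and t(3) errors, and gains clearly under skew. The sign depends on the distribution of change, on which the documents are silent. At 17 v 4 under normality, the t-test reaches 80% power only at a difference of about 1.64 SD.

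**The case against.** The strongest defence is that the plan is already modest. It calls the factors potential, heads the paragraph as exploratory, lists component 5 under feasibility and concedes low power. The power clause can also be read as explaining why the exploration is partly qualitative, which is a sensible response to 21 participants. The intervals above then only quantify an admitted weakness.

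Much of this stands, and it limits the severity. It does not answer the identification point. Those caveats disclose imprecision; none says that the quantity cannot be estimated without a comparator. The charitable reading of the power clause also leaves it attached to "non-parametric statistics given the lack of power".

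Two stronger readings are tempting, and neither is supported. A reader might infer that non-parametric tests necessarily make the power worse; the table shows that this holds for normal changes but not for skewed or heavy-tailed ones. A reader might also infer that a moderator will be named for the RCT, or dropped, according to significance. The documents contain no such rule. The consultation described under Study Design draws on family feedback, fidelity ratings and the performance of the measures, without mentioning moderators.

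Nor do the documents give the size of any difference in untreated change. The direction and amount of bias in this trial are therefore unknown.

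**Conclusion.** The point holds as a minor one. Component 5 of the primary aim and the Exploratory Analyses paragraph use a term that the design cannot support: with one arm, any association of sex, IQ, ASD or EF severity, or SES with pre-post change is a predictor of change. This follows from the design and rests on no numerical assumption. Separately, lack of power is not a valid reason for non-parametric statistics, although such statistics may be a good choice on other grounds.

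The intervals of about ±1.16 SD for sex and ±.43 for a correlation near zero assume full retention and, for sex, a 4 v 17 split with equal SDs; dropout would widen them. The regression-to-the-mean figures for EF severity depend on assumed reliabilities. The feasibility results and the main pre-post analysis are untouched.

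**What to change.** In the Purpose of Study and in the Exploratory Analyses paragraph:

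1. Replace *moderators* with *predictors of pre-post change*, and state that moderation can be assessed only in the future controlled trial.
2. For each factor, report the difference or slope in change, or a rank-based estimate, with a 95% CI, labelled as descriptive. For EF severity, add that regression to the mean is expected.
3. Remove lack of power as the reason for non-parametric methods. Where one is used, give small n, skew or outliers as the reason. Low power may stay as a stated limitation and as a reason for qualitative description.

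The cost is a few sentences and some intervals, with no new data, visits or participants. The downside is a more modest claim for a secondary exploratory analysis.
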